4.0 Test Schedule

Tests and procedures	Screening Phase		Active Monitoring Phase				
	≤28 days prior to randomization	≤7 days prior to randomization	Baseline (Prior to Cycle 1 Day 1 treatment)	Day 15 of each cycle ⁸ (± 3 days)	Prior to dosing on Day 1 of ≥ cy 2 (± 3 days)	Prior to dosing at restaging (C3 and every other cycle after)	End of Tx (within 30 days after last dose of study drug)
History and exam, wt, ECOG PS	X			X	X		X
Height	X						
Adverse event assessment	X			X ¹	X ¹		X
CBC/ differential: WBC, hemoglobin, hematocrit, platelets, neutrophil count, lymphocyte count, monocyte count, eosinophil count		X	X ¹¹	X	X		X
Chemistry: Sodium, potassium, chloride, CO ₂ , BUN, creatinine, glucose, calcium, SGOT (AST), SGPT (ALT), total bilirubin, alk phos, albumin, total protein		X	X ¹¹	X	X		X
Magnesium		X		X ⁵	X ⁵		X ⁵
Tumor Blood Bio-Markers (CEA)		X			X (C2 only)	X (at each restaging)	
Serum Pregnancy test ²		X	X ¹¹			X	
Tumor measurement (CT or MRI of the chest, abdomen and pelvis) ³	X					X	
COLOMATE Companion Trial Recommendation Form ¹²	X						
Mandatory blood sample – whole blood ^{4, 9,R}			X				
Mandatory blood sample – plasma ^{4,9,R}			X		X (C2 only)	X (at each restaging)	X
Mandatory tissue sample– archival tumor paraffin ^{6,R}			X				

Tests and procedures	Screening Phase		Active Monitoring Phase				
	≤28 days prior to randomization	≤7 days prior to randomization	Baseline (Prior to Cycle 1 Day 1 treatment)	Day 15 of each cycle ⁸ (± 3 days)	Prior to dosing on Day 1 of ≥ cy 2 (± 3 days)	Prior to dosing at restaging (C3 and every other cycle after)	End of Tx (within 30 days after last dose of study drug)
Mandatory Patient Questionnaire Booklet (Appendix II) ¹⁰			X		X		X
Patient Medication Diary (Appendix IV) ¹³					X	X	X
Optional Blood sample-cfDNA Guardant 360 ^{4,7,R}							X

- 1 The adverse event assessment will be evaluated at the end of each cycle prior to the beginning of the next cycle and at day 15 visit for the first 6 cycles. Please note: only the maximum grade will be needed for data entry.
- 2 For women of childbearing potential only. Must be done ≤ 7 days prior to randomization.
- 3 Use same imaging throughout the study.
- 4 Kits are required for this collection. Refer to Section 14.0.
- 5 Only for patients receiving panitumumab.

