- 6.16 Treatment cannot begin prior to randomization and must begin \leq 7 days after randomization.
- 6.17 Pretreatment tests/procedures (see Section 4.0) must be completed within the guidelines specified on the test schedule.
- 6.18 All required baseline symptoms (see Section 10.52) must be documented and graded.
- 6.19a Treatment on this protocol must commence at an ACCRU institution under the supervision of a medical oncologist.
- 6.19b Study drug is available on site.
- 6.19c Blood draw kit is available on site.

Exclusion: Guardant 360 kit does not need to be on site at the time of registration.

- 6.19d Patient questionnaire booklet is available on site; copies are not acceptable for this submission.

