8.0 Dosage Modification Based on Adverse Events

Subjects will be monitored continuously for AEs from the date of first dose of study drug and for 30 days after the last dose of study drug. Subjects will be instructed to notify their treating physician of any and all AEs. All AEs should also be managed with supportive care at the earliest signs of toxicity. Subjects should receive appropriate supportive care measures as deemed necessary by the Investigator. Suggested supportive care measures for the management of adverse events are outlined in Section 9.0.

Subjects experiencing one or more AEs due to study drug(s) may require dose modification(s) as described in Sections 8.1, 8.2, and 8.3. If multiple adverse events are seen, administer dose based on greatest reduction required for any single adverse event observed. Reductions or increases apply to treatment given in the preceding cycle and are based on adverse events observed since the prior dose. At the discretion of the Investigator, dose modifications are permitted outside of those provided in the protocol if the Investigator feels it is in the interest of the subject's safety (e.g., due to multiple toxicities, persistent toxicities, intercurrent illness, or short term compliance or monitoring issues, etc.). Subjects may need to be followed at least weekly when the study drug is held for clinically significant toxicity until the toxicity returns to Grade ≤ 1 or is determined to be controlled, chronic, or irreversible.

Dosing interruptions are permitted in the case of medical / surgical events or logistical reasons not related to study therapy (e.g., elective surgery, unrelated medical events, patient vacation, and/or holidays). Subjects should be placed back on study therapy within 4 weeks of the scheduled interruption, unless otherwise discussed with the Lead PI. The reason for interruption should be documented in the patient's study record.

ALERT: ADR reporting may be required for some adverse events (See Section 10)

8.1 Panitumumab: This section applies to adverse events associated with panitumumab. For adverse events associated with regorafenib, please refer to Section 8.2 and for TAS-102, please refer to Section 8.3.

* Located at [REDACTED]

** Use the following to describe actions in the Action column:

- Omit = Treatment is not given for this cycle
- Hold/Delay = Treatment can be made up as part of this cycle
- Discontinue = Treatment is totally stopped

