- **Dose Modifications – Dermatologic Toxicity**

➤ **Table 8.11. Dose Modifications during Vectibix Treatment**

Occurrence of Skin Symptom(s): \geq grade 3 ^a	Administration of Vectibix	Outcome	Dose Regulation
Initial occurrence	Stop 1 or 2 doses	Improved (< grade 3)	Continue infusion at 100% of original dose
		Not recovered	Discontinue
At the second occurrence	Stop 1 or 2 doses	Improved (< grade 3)	Continue infusion at 80% of original dose

		Not recovered	Discontinue
At the third occurrence	Stop 1 or 2 doses	Improved (< grade 3)	Continue infusion at 60% of original dose
		Not recovered	Discontinue
At the fourth occurrence	Discontinue	--	--

^a Greater than or equal to Grade 3 is defined as severe or life-threatening

Management of Skin Toxicities

Proactive skin treatment including skin moisturizer, sunscreen (SPF > 15 UVA and UVB), topical steroid cream (not stronger than 1% hydrocortisone) and an oral antibiotic (e.g., doxycycline), as prescribed by the physician, may be useful in the management of skin toxicities. Patients may be advised to apply moisturizer and sunscreen to face, hands, feet, neck, back and chest every morning during treatment, and to apply the topical steroid to face, hands, feet, neck, back and chest every night. Treatment of skin reactions should be based on severity and may include a moisturizer, sunscreen (SPF > 15 UVA and UVB), and topical steroid cream (not stronger than 1% hydrocortisone) applied to affected areas, and/or oral antibiotics, as prescribed by the physician.

Pulmonary Toxicity

In the event of acute onset or worsening of pulmonary symptoms, consider withholding panitumumab. If Interstitial Lung Disease is confirmed, discontinue panitumumab.

For Toxicities other than Dermatologic or Pulmonary

Withhold panitumumab for any grade 3 or 4 panitumumab-related toxicity with the following exceptions:

- Panitumumab will only be withheld for symptomatic grade 3 or 4 hypomagnesemia and/or hypocalcemia that persists despite aggressive magnesium and/or calcium replacement
- Panitumumab will only be withheld for grade 3 or 4 nausea, diarrhea, or vomiting that persists despite maximum supportive care.

Diarrhea management (refer to the 9.4 for management)

Electrolytes

Subjects should be evaluated and managed as per local medical practice. If hypomagnesemia is present, replacement should be managed with either oral and/or parenteral replacement, according to

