11.0 Treatment Evaluation Using RECIST Guideline

NOTE: This study uses protocol RECIST v1.1 template dated 2/16/2011. See the footnote for the table regarding measureable disease in Section 11.44, as it pertains to data collection and analysis.

Response and progression will be evaluated in this study using the new international criteria proposed by the revised Response Evaluation Criteria in Solid Tumors (RECIST) guidelines (version 1.1) [38]. Changes in the largest diameter (unidimensional measurement) of the tumor lesions and the short axis measurements in the case of lymph nodes are used in the RECIST guideline.

11.1 Schedule of Evaluations: For the purposes of this study, patients should be reevaluated every 8 weeks.

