11.43 Response Criteria

11.431 All target lesions and target lymph nodes followed by CT/MRI must be measured on re-evaluation at evaluation times specified in Section 11.1. Specifically, a change in objective status to either a PR or CR cannot be done without re-measuring target lesions and target lymph nodes.

Note: Non-target lesions and non-target lymph nodes should be evaluated at each assessment, especially in the case of first response or confirmation of response. In selected circumstances, certain non-target organs may be evaluated less frequently. For example, bone scans may need to be repeated only when complete response is identified in target disease or when progression in bone is suspected.

11.432 Evaluation of Target Lesions

- Complete Response (CR): All of the following must be true:
 - a. Disappearance of all target lesions.
 - b. Each target lymph node must have reduction in short axis to <1.0 cm.
- Partial Response (PR): At least a 30% decrease in PBS (sum of the longest diameter for all target lesions plus the sum of the short axis of all the target lymph nodes at current evaluation) taking as reference the PBS (see Section 11.41).
- Progression (PD): At least one of the following must be true:
 - a. At least one new malignant lesion, which also includes any lymph node that was normal at baseline (< 1.0 cm short axis) and increased to \geq 1.0 cm short axis during follow-up.
 - b. At least a 20% increase in PBS (sum of the longest diameter for all target lesions plus the sum of the short axis of all the target lymph nodes at current evaluation) taking as reference the MSD (Section 11.41). In addition, the PBS must also demonstrate an absolute increase of at least 0.5 cm from the MSD.
 - c. See Section 11.32 for details in regards to the requirements for PD via FDG-PET imaging.
- Stable Disease (SD): Neither sufficient shrinkage to qualify for PR, nor sufficient increase to qualify for PD taking as reference the MSD.

11.433 Evaluation of Non-Target Lesions & Non-target Lymph Nodes

- Complete Response (CR): All of the following must be true:
 - a. Disappearance of all non-target lesions.

- b. Each non-target lymph node must have a reduction in short axis to <1.0 cm.
- Non-CR/Non-PD: Persistence of one or more non-target lesions or non-target lymph nodes.
- Progression (PD): At least one of the following must be true:

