14.0 Body Fluid Biospecimens

14.1 Summary Table of Research Blood/Blood Products to Be Collected for This Protocol

Indicate if specimen is mandatory or optional	Collection tube description and/or additive (color of tube top)	Volume to collect per tube (number of tubes to be collected)	Blood product being processed and submitted by participating site	Baseline ¹	Prior to dosing on Day 1 of Cycle 2	Restaging ²	End of Treatment ³	Additional processing required at site after blood draw?	Storage /shipping conditions ⁴
Mandatory	EDTA K2 (Purple)	10 mL (1)	Whole Blood	X				No	Freeze /dry ice
Mandatory	EDTA K2 (Purple)	10 mL (4)	Platelet Poor Plasma and	X	X	X	X	Yes	Freeze /dry ice

			White blood cells					
Optional	Streck tube ⁵	10 mL (2)	Whole blood			X	No	Room temperature

1. May occur prior to treatment on Cycle 1 Day 1.
2. At time of radiographic assessments (i.e., every other cycle beginning on cycle 3) which may occur \leq 14 days prior to day 1 of new cycle (estimated 4 restagings per patient).
3. Discontinuation of study treatment.
4. After all samples have been processed according to kit instructions, ship all specimens according to shipping instructions (see Section 14.3 for detailed shipping instructions.) Patients have the option to complete cfDNA testing at study completion and are encouraged to re-register with protocol ACCRU-GI-1611. See section 13.7.

14.2 Kits are required for this study.

NOTE: You will be ordering and receiving kits from two different locations.

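### Restaging scans run on two clocks, cycle starts (4.0, 14.1) and every 8 weeks (11.1), and no sentence keeps them on the calendar when a cycle start slips

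*Combined protocol and SAP*

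**What the plan says.** - **Cycle clock.** The test schedule in 4.0 marks tumor measurement in the column headed "Prior to dosing at restaging (C3 and every other cycle after"). Footnote 2 of 14.1 ties the restaging blood samples to the same scans: "At time of radiographic assessments (i.e., every other cycle beginning on cycle 3) which may occur" up to 14 days before day 1 of the new cycle.
- **Calendar clock.** Section 11.1 reads: "For the purposes of this study, patients should be reevaluated every 8 weeks". It states no starting point and no window. Section 11.431 refers to it: target lesions "must be measured on re-evaluation at evaluation times specified in Section 11.1".
- **PFS origin.** Section 16.51 measures PFS from randomization to documented progression or death. Section 6.16 says "Treatment cannot begin prior to randomization and must begin" within 7 days after randomization. The baseline scan falls within 28 days before randomization (4.0).
- **Delays.** For TAS-102, 8.3 has rows for low counts at cycle start, where treatment waits for recovery. For interruptions unrelated to study therapy, 8.0 says: "Subjects should be placed back on study therapy within 4 weeks of the scheduled interruption". Other rules need not move the next day 1: "Hold/Delay = Treatment can be made up as part of this cycle" (action definitions in Section 8), and "Stop 1 or 2 doses" for panitumumab skin toxicity (Table 8.11).
- **Endpoints.** PFS (2.21) and the clinical benefit rate, which counts stable disease of 6 months or more (2.23), are secondary. Their p-values are descriptive (16.5).

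**The concern.** PFS is dated to the scan that documents progression. The plan's control PFS of about 1.9 months (16.1) is roughly one scan interval, so many progressions will be dated by the first or second restaging scan. If scans follow the cycle, a late cycle start postpones the scan and with it the recorded progression. If late starts are more common in one arm, that arm's PFS looks longer without any difference in disease control. Stable disease of 6 months or more can shift the same way. Treatment is known to the sites and the toxicity rules differ by drug, so unequal delay is plausible, but the documents give no rates.

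**Working it through.** **1. Do the schedules agree without delay?** Yes. Cycle length is 28 days (Schema), so 2 x 28 = 56 = 8 x 7 days. C3, C5, C7 and C9 start 56, 112, 168 and 224 days after C1 day 1, which is weeks 8, 16, 24 and 32. Control PFS of 1.9 months is 1.9 x 30.44 = 57.8 days, against a 56-day interval.

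**2. When do they conflict?** Let d be the total delay up to C3, counting from C1 day 1. Sections 4.0 and 14.1 allow the first restaging scan from day 56 + d - 14 to day 56 + d; 11.1 asks for day 56.

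| d (days) | Allowed by 4.0 and 14.1 | Is day 56 inside? |
|---|---|---|
| 0 | 42-56 | yes |
| 7 | 49-63 | yes |
| 14 | 56-70 | yes, at the edge |
| 28 | 70-84 | no |

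All three passages can be met while d is 14 or less. Nothing obliges a site to use the early window, and a scan on the new day 1 also satisfies 4.0. Counted from randomization, a treatment start on day 7 adds 7 days to each date in the middle column. Delays accumulate, so later scans can pass the 14-day limit when the first does not.

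**3. Which delays move day 1?**
- TAS-102, 8.3 cycle-start rows: explicitly.
- Regorafenib, 8.2: the 4-week wording concerns a hold, which the action definitions allow to be made up within the cycle.
- Panitumumab, Table 8.11: doses are stopped; the text does not say that the next day 1 moves.
- All drugs, 8.0: up to 4 weeks, but only for reasons not related to study therapy.

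**4. Size, under assumed delay rates.** Simulation with the same true PFS in both arms: exponential, median 1.6-1.9 months including deaths, death median 6.5 months, treatment start uniform over 0-7 days. Each cycle start moves by 1 or 2 weeks with the stated probability. The HR is panitumumab versus control; with no scan-timing effect it is 1.00.

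| Scans | Which arm is delayed more | HR |
|---|---|---|
| Follow the cycle | control (panitumumab/control 0/25%, 0/50%, 15/25%, 25/50% of cycles) | about 1.03-1.15 |
| Held to the 8-week dates where the 14-day window allows | control, same rates | 1.01-1.04 (1-week delays), 1.05-1.08 (2-week delays) |
| Follow the cycle | panitumumab (25/15%, 50/25%) | 0.92-0.98 |
| Follow the cycle | equal | 1.00 |
| Every 8 weeks from randomization, plus or minus 7 days | either | 1.00 |

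The figures depend on the model. Reading 1.6-1.9 months as the median to progression alone raises the control-only case to about 1.24. A true median of 4.0 months (the figure in 1.3 for patients *RAS* wild-type in blood) brings the HR to 0.98-1.04.

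**5. Against sampling error.** With 53 per arm the SD of the log HR is about 0.20, so the 95% factor is exp(1.96 x 0.20) = 1.48 either way.

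**6. Stable disease of 6 months or more.** Section 16.53 does not give 6 months in days. With an assumed 182.6-day cutoff, delay changes the share progression-free past 6 months by -0.3 to +4.3 points; 0.043 x 53 = 2.3, so about 0 to 2 patients per arm.

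**The case against.** The strongest reply is that the plan already answers the question. Section 11 defines response and progression, 11.431 says lesions must be measured at the times in 11.1, and 11.1 is a calendar interval. The 14-day window also lets sites keep week 8 through modest delays. Many holds never move day 1. The endpoints involved are secondary with descriptive p-values, and imaging by cycle is a legitimate choice.

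Most of this stands and limits the point. It does not remove it: 4.0 is the schedule that sites work from, 11.1 has no origin or window, and no sentence says that scans stay on the calendar when a cycle slips.

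Three stronger readings are tempting and not supported:
- **Any delay puts the passages in conflict.** It does not; up to 14 days they can all be met (step 2).
- **The 4-week interruption shows a 28-day bias between arms.** It can put a cycle-tied scan at day 84 instead of day 56, but 8.0 confines it to reasons not related to study therapy, for all drugs. That gives no reason to expect an arm difference, and equal delay gives an HR of 1.00.
- **No scan is linked to randomization.** The baseline scan is, and 6.16 limits how late treatment can start. Only the restaging scans lack an anchor.

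**Conclusion.** The point holds in limited form. Two imaging clocks agree without delay, can both be met up to 14 days of cumulative delay, and conflict beyond that. Neither is anchored to the PFS origin. If day-1 delays differ by arm, secondary PFS and stable disease of 6 months or more carry some scan timing. The HR ranges in step 4 rest on assumed delay rates, and they are small beside a sampling factor of about 1.5. A reader might infer that the bias favors one arm. The documents do not support that: only the TAS-102 rows clearly move day 1, the share of control patients on TAS-102 is left to the physician within the prior-treatment limits (7.12), and delays on panitumumab would act the other way. Nor is the main conclusion at risk: the OS comparison, its power and the futility rule do not use scan dates. Low severity; worth correcting because it is cheap.

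**What to change.** Reconcile 4.0, 11.1 and footnote 2 of 14.1 to one imaging schedule for both arms: every 8 weeks from randomization, with one stated window (for example plus or minus 7 days), kept regardless of cycle delays or holds. State whether the restaging plasma and CEA samples follow the scan or the cycle visit.

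The cost is protocol wording plus a practical burden: some scans will not coincide with a cycle visit, so the timing of the other items in the 4.0 restaging column must be reworded. No treatment rule changes.

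Separate minor point: 4.0 marks no tumor measurement at end of treatment, while 18.1 expects RECIST measurements then. For patients who stop without progression, 18.1 collects disease status every 3 months but no imaging interval is given. Reconcile these and state one interval, the same in both arms, because 16.51 censors PFS at the last disease evaluation.

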- 6 Receipt of archival tumor tissue is not required for study randomization and initiation of therapy. However, it is mandatory to receive the required tissue within 90 days from randomization. See section 17.0.
- 7 Patients have the option to complete cfDNA testing at study completion and will be allowed to re-register with protocol ACCRU-GI-1611. Site will access results by creating an account at [REDACTED] Sites will be notified by Guardant Health via email when results are available in the portal. Refer to Section 13.7. See detailed instructions on the ACCRU website under Manuals and Forms.
- 8 May discontinue day 15 visit beginning cycle 7. Additional visits and laboratory studies are permitted as per institutional practice and as clinically appropriate.
- 9 Patient must be registered prior to collection.
- 10 Patient questionnaire will be completed at baseline and each cycle (Appendix II). Patient questionnaire booklets **must** be used; copies are not acceptable for this submission. The booklet order form is located on the ACCRU website under Manuals and Forms.
- 11 If screening tests occur ≤ 7 days prior to C1D1, they do not have to be repeated prior to dosing.
- 12 The COLOMATE Companion Trial Recommendation Form must indicate that the patient has met molecular eligibility to screen. The patient must be registered to the companion study ≤30 days from date of COLOMATE Companion Trial Recommendation Form completion. If the COLOMATE Companion Trial Recommendation Form recommends a different companion study, patient may still enroll.
- 13 The diary must begin the day the patient starts taking the medication and must be completed per protocol and returned to the treating institution OR compliance must be documented in the medical record by any member of the care team.

R Research funded.

Event Monitoring: survival follow-up will be done every 3 months (± 7 days) until 3 year after randomization.

5.0 Stratification Factors:

- 5.1 Primary tumor location: right (cecum, ascending colon, hepatic flexure, and transverse colon) vs left (splenic flexure, descending colon, sigmoid colon, rectosigmoid junction, and rectum).
- 5.2 Prior TAS-102 or regorafenib: Yes vs No.

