6.0 Registration/Randomization Procedures

6.1 Registration Procedures

- 6.11 To register a patient, fax (██████████) a completed eligibility checklist to the Academic and Community Cancer Research United (ACCRU) Registration Office between 8 a.m. and 4:30 p.m. central time Monday through Friday.

NOTE: ACCRU-GI-1611 (COLOMATE) treating physician will provide COLOMATE Companion Trial Recommendation Form which will include the Patient ID that must be used for this study.

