Appendix II: ACCRU-GI-1623 LINEAR ANALOGUE SELF ASSESSMENT

Patient Name: _____ Date: _____
Patient Number: _____

Directions: Please circle the number (0-10) best reflecting your response to the following that describes your feelings **during the past week, including today**.

How would you describe:

1. your overall Quality of Life?

2. your overall mental (intellectual) well being?

3. your overall physical well being?

0 1 2 3 4 5 6 7 8 9 10
As bad as
it can be As good as
it can be

4. your overall emotional well being?

0 1 2 3 4 5 6 7 8 9 10
As bad as
it can be As good as
it can be

5. your level of social activity?

0 1 2 3 4 5 6 7 8 9 10
As bad as
it can be As good as
it can be

6. your overall spiritual well being?

0 1 2 3 4 5 6 7 8 9 10
As bad as
it can be As good as
it can be

7. the frequency of your pain?

A horizontal scale with numerical labels from 0 to 10. The label 'No pain' is positioned above the 0 mark, and the label 'Constant pain' is positioned above the 10 mark.

8. the severity of your pain, on the average?

9. your level of fatigue, on the average?

A horizontal scale with numerical labels from 0 to 10. The label 'No fatigue' is positioned above the 0 mark, and the label 'Constant' is positioned below the 10 mark.

Tiredness

10. your level of support from friends and family?

11. your financial concerns?

12. your legal concerns (will, advanced directives, etc.)?

© 1996 Mayo Foundation for Medical Research

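### The test schedule does not require the baseline LASA before randomization, so the quality-of-life baseline can be given with the treatment arm already known

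*Combined protocol and SAP*

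**What the plan says.** Goal 2.25 is a comparison of quality of life between the arms using the LASA questionnaire.

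- **Schedule (Section 4.0).** The row "Mandatory Patient Questionnaire Booklet (Appendix II" is marked at baseline, before dosing on Day 1 from cycle 2 onward, and at end of treatment. The baseline mark is in the column "Baseline (Prior to Cycle 1 Day 1 treatment", the first column of the Active Monitoring Phase. The two Screening Phase columns, at most 28 and at most 7 days before randomization, are empty for this row.
- **Footnote 10.** "Patient questionnaire will be completed at baseline and each cycle (Appendix II"). It does not refer to randomization.
- **Section 6.16.** "Treatment cannot begin prior to randomization and must begin" within 7 days after it.
- **Sections 6.22, 7.11 and 7.12.** Allocation follows registration. Arm A is intravenous panitumumab; Arm B is TAS-102 or regorafenib tablets, chosen by the treating physician. No blinding is described.
- **Appendix II.** The recall period is "during the past week, including today".
- **Section 16.55.** The specified analysis is a plot of the mean of item 1 (overall quality of life) at each cycle, by arm. Further analyses are optional and undefined. Section 16.5 makes secondary p-values descriptive.

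**The concern.** A baseline is useful in a randomized comparison because the assignment cannot have influenced it. Once a patient knows the arm, a self-rated score can move in response to that news. LASA asks for overall quality of life, emotional well-being and financial concerns. The last could respond to assignment because Section 19.31 says panitumumab is supplied and the control drugs are not.

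If the baseline can be answered after allocation, a difference between the arms at that point could be chance or a reaction to the assignment, and the data could not tell them apart. A change-from-baseline or baseline-adjusted analysis would then use a variable measured after randomization, and could hide or create part of an arm difference. A patient who leaves between allocation and first treatment might also not have completed the booklet.

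**Working it through.** The plan states no figure on this point, so there is none to reproduce. The check is to set the relevant provisions side by side and then bound the exposure.

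**1. Is completion before allocation required anywhere?**

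| Place | What it fixes | Timing relative to allocation |
|---|---|---|
| 4.0, column with the LASA baseline mark | Before cycle 1 Day 1 treatment | Upper limit only; the phase heading suggests after |
| 4.0, footnote 10 | Baseline and each cycle | Silent |
| 6.14, checks before a randomization is accepted | IRB approval, eligibility, consent, authorization | Booklet not listed |
| 6.19d | Booklet on site | Possible before, not required |
| 18.1, initial materials | Submission within 2 weeks after registration | A submission deadline, not a completion time |

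None requires it. By contrast, history and performance status, adverse events, blood counts, chemistry, CEA and imaging all have a mark in a pre-randomization column.

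**2. Is completion after allocation required anywhere?** No. Footnote 9, "Patient must be registered prior to collection", is attached to the blood-sample rows and not to the booklet row. Footnote 11 lets screening laboratory tests count for the same Baseline column, so a mark there does not by itself mean after allocation. Either order complies.

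**3. How much of the recall week can fall after allocation?** Let k be the number of days from allocation to the booklet. By Section 6.16, k runs from 0 to 7 for a treated patient whose booklet follows allocation. The recall covers 7 days including the day of completion, so the share lying after the day of allocation is k/7:

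- k = 0: 0/7 = 0%
- k = 3: 3/7 = 43%
- k = 7: 7/7 = 100%

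A booklet completed before allocation has a share of 0%. The documents give no distribution of k. Even at k = 0 the patient may know the arm when answering, so the share describes recall, not the size of any bias.

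**4. How many baselines could be missing through cancellation?** Section 16.2 allows 14 patients above 106, and 106 + 14 = 120. That is 14/120 = 11.7% of maximum accrual, for ineligibility, cancellation, major violation and other reasons together. The number who leave because of their assignment is not given, so under this allowance the range is 0 to 14.

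**5. Which analyses use the baseline?** In the Section 16.55 plot, only the baseline point. Each later mean is computed from that cycle's scores and does not involve the baseline. The optional further analyses could use it.

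**The case against.** The strongest reply is that the plan leaves the timing open rather than wrong. A site that has the booklet completed before randomization complies, and Section 6.19d makes that feasible. This stands, so three stronger readings that a reader might draw are not supported:

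- **That the baseline is always taken after allocation.** The phase heading suggests it, but the column sets only an upper limit. It is also unsupported to say that every patient's baseline is affected.
- **That the baseline is missing for those who leave on learning their arm.** Section 13.6 still requires on-study material from patients who cancel, and Section 18.1 lists the baseline booklet among the initial materials. Whether on-study material includes the booklet is unclear. Missing baselines are possible, not stated. These patients have no on-treatment scores, so losing their booklets would change little beyond the baseline mean.
- **That the planned quality-of-life comparison is biased.** The plan specifies no change from baseline and no baseline adjustment. The one specified analysis is descriptive, and its later points do not depend on the baseline.

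The reply does not close the gap. Leaving the order to each site means timing may vary without control. Goal 2.25 is a comparison between arms, the baseline is the natural reference for reading the plot, and the further analyses that Section 16.55 permits could use it.

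**Conclusion.** The point holds in a limited form. The schedule does not require the baseline LASA before randomization and lists it where sites are likely to complete it afterwards. The score can therefore be given with the arm known, and may be missing for some patients who cancel before treatment.

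From 0 to 7 days of a 7-day recall can fall after allocation. What is exposed is the baseline point of the by-arm plot and any change-from-baseline or baseline-adjusted analysis for goal 2.25. Overall survival, its sample size and its decision rules are untouched, as are the post-baseline means. The documents support no estimate of a shift in points, nor of its direction.

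Two assumptions carry this. Patients learn their arm at or soon after allocation; this is inferred from the treatments and from the absence of any blinding, because the protocol does not call this trial open-label. And some sites will follow the phase heading and use the booklet after allocation. This is a low-cost improvement to a secondary endpoint, not a flaw in the main design.

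**What to change.** Make two edits in Section 4.0.

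1. Move the baseline mark in the questionnaire row to the Screening Phase column "≤7 days prior to randomization".
2. Add to footnote 10: *The baseline booklet is completed after consent and before randomization.*

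Leave the later-cycle and end-of-treatment booklets as they are. The booklet need not become a condition for accepting a randomization under Section 6.14.

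The 7-day column matters. With up to 7 days from randomization to treatment, the baseline would be at most about 7 + 7 = 14 days old at first dose. The 28-day column would allow 28 + 7 = 35 days, which is long for patients who need a life expectancy of only 3 months (Section 3.19a).

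The change adds no visit and no instrument. The booklet must already be on site (6.19d), ability to complete questionnaires is already an eligibility criterion (3.19f), and the identifier exists beforehand: the COLOMATE recommendation form is the one "which will include the Patient ID that must be used for this study" (6.11). The costs are a few booklets from patients who then fail screening and the interval of up to about 14 days. A baseline not taken before allocation cannot be recovered later, so the edit helps only patients randomized after it takes effect.
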